10.8.6 European Union

10.8.6.1 Safety reporting to the agency

In the EU, the Sponsor will comply with safety reporting requirements and procedures as described in the European Clinical Trials Regulation No 536/2014. All SUSARs to IMP will be reported to the EudraVigilance database within the required regulatory timelines.

A single Annual Safety Report, aligned with ICH E2F, will include safety information for all IMPs (including the reference compound[s]).

Safety reporting with regard to authorized AxMPs shall be made in accordance with Chapter 3 of Title IX of Directive 2001/83/EC, irrespective if they are used in accordance with the terms of the marketing authorizations of these products. The Investigator is requested to report any suspected adverse reactions assessed as solely related to an authorized AxMP to the National Competent Authority via the national reporting system.

10.9 APPENDIX 9: CONTINGENCY MEASURES FOR A REGIONAL OR NATIONAL EMERGENCY THAT IS DECLARED BY A GOVERNMENTAL AGENCY

Continuation of the study in the event of a regional or national emergency declared by a governmental agency:

- A regional or national emergency declared by a governmental agency (eg, public health emergency, natural disaster, pandemic, terrorist attack) may prevent access to the clinical trial site.
- Contingency procedures are suggested in this appendix and in [Section 8](#), for an emergency that prevents access to the study site, to ensure the safety of the participants, to consider continuity of the clinical study conduct, protect trial integrity, and assist in maintaining compliance with GCP in Conduct of Clinical Trials Guidance. Sponsor agreement **MUST** be obtained prior to the implementation of these procedures for the duration of the emergency.
- During the emergency, if the site will be unable to adequately follow protocol mandated procedures, alternative treatment outside the clinical trial should be postponed, and screening/enrollment, and administration of study intervention may be temporarily delayed/halted.

- For a regional or national emergency declared by a governmental agency, contingency procedures may be implemented for the duration of the emergency. The participant or their legally authorized representative should be verbally informed prior to initiating any changes that are to be implemented for the duration of the emergency (eg, study visit delays/intervention extension, use of local laboratories).

Attempts should be made to perform all assessments in accordance with the approved protocol to the extent possible. In case this is not possible due to a temporary disruption caused by a regional or national emergency, focus should be given to assessments necessary to ensure the safety of participants and those assessments important to preserving the main scientific value of the study. Procedures to be considered in the event of a regional or national emergency declared by a governmental agency for the duration of the emergency (after Sponsor agreement is obtained):

- The DTP supply of itepekimab/placebo from the Sponsor where allowed by local regulations and agreed upon by the participant.
- If on-site visits are not possible for visits other than Screening visit (Visit 1 [Week -3 to -5]) and enrollment visit (Visit 2 [Week 0]), remote visits (eg, with home nurses, home health vendor) may be planned for the collection of possible safety and/or pharmacodynamic data. Vital signs, hematology and clinical chemistry, routine urine analysis plus dipstick test (pregnancy) and AE reporting should have priority from a safety perspective.
- If on-site visits are not possible, visit windows may be extended for assessment of safety and/or pharmacodynamic data that cannot be obtained remotely (eg, spirometry visit window +/- 2 weeks for the IMP intervention period, and +/- 2 weeks for the visits during the post IMP intervention follow-up period).
- Use of local clinic or laboratory locations may be allowed for hematology and clinical chemistry samples.

Contingencies implemented due to a regional or national emergency will be documented.

If in case of unforeseen circumstances, a decision for each individual participant to remain and/or start in the study has to be made; this should be done on a case-by-case basis by the Investigator based on his/her best medical judgment. Clinical judgment of the treating physician should guide the management plan of each participant based on individual benefit/risk assessment.

All applicable local laws, institutional, and IEC/IRB regulations regarding study visits should be followed. Local guidelines related to Personal Protective Equipment use should also be followed. As previously mentioned, attempts should be made to perform all assessments in accordance with the protocol, but only if and when possible. Investigators should closely monitor and document all deviations to the study protocol and share them with the Sponsor contact on a real-time basis.

For Germany contingency measures are currently only applicable for the COVID-19 pandemic.

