5.5 CRITERIA FOR TEMPORARILY DELAYING

During a regional or national emergency declared by a governmental agency, if the site is unable to adequately follow protocol-mandated procedures, contingency measures are proposed in Appendix 9: ([Section 10.9](#): Contingency measures for a regional or national emergency that is declared by a governmental agency) should be considered for screening/enrollment/randomization/administration of study intervention.

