6.9 PRIOR AND CONCOMITANT THERAPY

Any medication or vaccine (including over-the-counter or prescription medicines, recreational drugs, vitamins, and/or herbal supplements) that the participant is receiving at the time of enrollment or receives during the study must be recorded along with:

- Reason for use.
- Dates of administration including start and end dates.
- Dosage information including dose route and frequency.

The Sponsor should be contacted if there are any questions regarding concomitant or prior therapy.

The following concomitant treatments are not permitted during the screening period and the randomized treatment period:

- Anti-IL5 or IL5R mAb (eg, benralizumab, mepolizumab, reslizumab, depemokimab).
- Anti-TSLP (tezepelumab).
- Anti-IgE therapy (eg, omalizumab).
- Anti-IL4 receptor mAb (eg, dupilumab).
- Other mAbs including anti-IL6, anti-IL17, anti-IL23, anti-IL12/23, anti-IL13, etc.
- Systemic immunosuppressants (eg, methotrexate, any anti-TNF mAbs, B and/or T-cell targeted immunosuppressive therapies, JAK inhibitors).
- Other investigational drugs.
- Live-attenuated vaccines (Appendix 15 [Section 10.15](#)).
- Allergen immunotherapy (except if initiated more than 3 months prior to Visit 1 and dose stable 1 month prior to Visit 1).
- INCS drops or sprays other than MFNS (except in Japan and China).
- Long-term courses (>2 weeks) of SCS.
- Initiation of maintenance antibiotic therapy is prohibited.
- Xhance, device.

- Intranasal emitting devices/ stents.
- Initiation of leukotriene antagonists/modifiers unless on stable dose for ≥ 30 days prior to Screening (Visit 1).
- Oral or intranasal decongestants other than single use during endoscopy as below.

Participants who between Visit 1 and Visit 2 receive any of the prohibited treatments, or treatment with SCS (oral, IV, IM, SC) or undergo surgery will not be randomized. They may however be re-screened following the procedures described in [Section 10.1](#).

The following is a list of concomitant medications that are permitted during the study:

- Nasal normal saline.
- Single intranasal decongestants administration eg, oxymetazoline hydrochloride (to reduce the swelling and widen the path for the endoscope), as well as a topical anesthetic, eg, lidocaine are allowed before endoscopy.
- Short-acting beta-agonist (SABA), LABA, and LAMA.
- Methylxanthines (eg, theophylline, aminophyllines).
- Inhaled CSs.
- Systemic antihistamines.

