6.9.1 Rescue therapy

During the study treatment and follow-up periods, based on clinical evaluation, in case of worsening of signs and/or symptoms/acute sinusitis requiring medical intervention, the Investigator may consider rescue treatment with:

- Systemic antibiotics (up to 2 weeks) in case of acute infection.
- Short course SCS (prednisone or equivalent prednisolone up to 7 days; avoid use 4 weeks before Week 24 or Week 52, if possible).
- Sinonasal surgery for CRSwNP (8 weeks of IMP treatment is recommended prior to surgery to allow onset of treatment effect).

Participants receiving rescue treatment other than surgery during the study should continue on study drug unless the Investigator decides to withdraw the study treatment. Before starting treatment with SCS participants should come to the study site for the clinical assessments. It is recommended to avoid use of SCS as rescue therapy during the Week 20 to Week 24. If a participant must use SCS during this period to control worsening of symptoms based on Investigator judgment the site should make every effort to schedule the Week 24 CT scan prior to SCS rescue therapy. For participants who undergo or are planned for surgery for CRSwNP, the Investigator may decide to continue IMP up to the time of surgery or EOT, whichever date

comes first. At the time of surgery participants will be permanently discontinued from study intervention and assessed as soon as possible using the procedures normally planned for the EOT visit. In any case participants who prematurely discontinued the intervention will be encouraged to return to the study site for the efficacy and safety assessments planned at EOT visit and for additional visits. Additional appropriate medical/therapy per local guideline or per Investigators decision may be considered to use as rescue medicine.

The date and time of rescue medication administration as well as the name and dosage regimen of the rescue medication must be recorded in the eCRF.

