- Serum ALT > 3 × ULN and total bilirubin > 2 × ULN (see Appendix 6 [[Section 10.6](#)]).
- Serum ALT > 5 × ULN if baseline ALT ≤ 2 × ULN or ALT > 8 × ULN if baseline ALT > 2 × ULN (see Appendix 6 [[Section 10.6](#)]).

Any abnormal laboratory value or ECG parameter will be immediately rechecked for confirmation (within 48 hours) before making a decision of permanent discontinuation of the IMP for the concerned participant.

In case of exposure to prohibited concomitant medication such as, but not limited to immunomodulating mAb or immunosuppressants as listed in the prohibited medications from [Section 6.9](#), a decision should be made on the need for temporary or permanent discontinuation of IMP. The decision to resume the treatment with IMP will be made by the Investigator based on the clinical judgment and potential risks of drug interactions.

Handling of participants after permanent intervention discontinuation

Participants will be followed-up according to the study procedures specified in this protocol up to the scheduled date of study completion, or up to recovery or stabilization of any AE to be followed-up as specified in this protocol, whichever comes last.

If possible, and after the permanent discontinuation of intervention, the participants will be assessed using the procedure normally planned for ETD Visit.

In addition, and to allow assessment of participant outcomes over the stipulated study period, participants will be asked and encouraged to complete all remaining study treatment visits and participate in all safety follow-up assessments according to the visit schedule with a +/- 5-day window.

For such participants the assessment schedule may be reduced. For site visits, under exceptional circumstances when a participant cannot or does not want to come to the site for a scheduled visit, a phone contact can be made. During the phone contact, at least information about AEs, concomitant medications, and exacerbation events should be collected.

All cases of permanent intervention discontinuation must be recorded by the Investigator in the appropriate pages of the eCRF when considered as confirmed.

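### Section 10.9 advises postponing treatment outside the trial in a declared emergency, without an exception for medical need and in tension with the appendix's own safety aim and benefit/risk clause (minor)

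*Protocol*

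**What the plan says.** Section 10.9 applies when an emergency declared by a governmental agency may block access to the trial site. It presents its procedures as suggestions, requires Sponsor agreement before they are used, and offers them "for an emergency that prevents access to the study site, to ensure the safety of the participants", among other aims.

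One bullet deals with a site that cannot adequately carry out the protocol during the emergency. In that case, "alternative treatment outside the clinical trial should be postponed, and screening/enrollment, and administration of study intervention may be temporarily delayed/halted". The bullet gives no exception for medical need and does not refer to the rescue provisions.

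Later in the same appendix, after a sentence on deciding case by case whether a participant stays in or starts the study, the text reads: "Clinical judgment of the treating physician should guide the management plan of each participant based on individual benefit/risk assessment".

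**The concern.** The bullet joins two things that should not go together. It lets the site halt study drug or enrollment, and it also advises that treatment elsewhere be put off. Participants in this trial have inadequately controlled disease (Section 5.1 asks for a bilateral polyp score of at least 5 of 8, moderate or severe congestion at Visit 1, and prior sinonasal surgery or a need for systemic corticosteroids), so a need for other treatment during a pause is foreseeable.

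What is at stake is participant care. A site following the bullet to the letter could delay treatment that the treating physician would otherwise give, and the appendix does not say which of its two recommendations prevails.

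**Working it through.** No arithmetic applies. The check is a comparison of the relevant texts.

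1. **The instruction (Section 10.9).** "alternative treatment outside the clinical trial should be postponed" carries no condition beyond the emergency and the site's inability to follow procedures. In the same sentence, trial activities *may* be delayed or halted, while outside treatment *should* be postponed. The firmer verb is attached to the participant's care.

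2. **The aim (Section 10.9).** Participant safety is the first purpose named for the contingency procedures. Deferring outside care while study drug is halted does not serve that purpose unless the care is not needed, and the bullet does not make that distinction.

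3. **The benefit/risk clause (Section 10.9).** "Clinical judgment of the treating physician should guide the management plan of each participant based on individual benefit/risk assessment" points towards individual judgment. Neither this clause nor the postponement bullet is made subject to the other. Both are recommendations, so this is a tension and not a flat contradiction.

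4. **The section that sends sites here (Section 5.5).** In the same situation it says contingency measures "should be considered for screening/enrollment/randomization/administration of study intervention". Those are all trial activities. Its silence on outside treatment does not contradict Section 10.9, but it gives the postponement advice no support.

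5. **The nearest comparable rule (Section 10.1.9).** If the whole study is prematurely terminated or suspended, the Investigator is to see that participants get appropriate therapy or follow-up. A pause at a site is not the same event, but a participant off study drug is in a similar position, and the advice runs the other way.

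6. **Can a participant be off study drug when the bullet applies?** Yes. Section 7.1.3 names disruption from a declared emergency as a ground for temporary discontinuation.

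7. **Who keeps access to treatment?**
   - *Randomized participants.* Section 6.9.1 opens with "During the study treatment and follow-up periods, based on clinical evaluation" and allows antibiotics, short-course systemic corticosteroids, sinonasal surgery and other therapy by local guideline or the Investigator's decision. Nothing in Section 10.9 suspends this.
   - *Participants in screening.* Section 6.9.1 does not cover them. However, the Section 1.3 footnote on the 28 ± 7 day screening period expressly contemplates rescue with systemic corticosteroids or surgery in that period, and Section 6.9 covers the same treatments and prohibited medication between Visit 1 and Visit 2. The consequence is that the participant is not randomized; Section 6.9 allows re-screening. Neither provision bars care.
   - *Participants exposed to prohibited medication on treatment.* Section 7.1.1 says "a decision should be made on the need for temporary or permanent discontinuation of IMP". That is a decision about study drug, not a bar on care.

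The protocol's ordinary rules therefore leave treatment open at every stage. The Section 10.9 bullet is out of step with them.

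**The case against.** The strongest reply is that the appendix should be read as a whole. The benefit/risk clause covers each participant's management plan and can be taken to supply the missing medical-need exception. The procedures are only suggested, need Sponsor agreement and apply only in a declared emergency. The bullet may also be meant merely to discourage a switch to a competing therapy during a short pause.

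Much of this stands. It limits the exposure and rules out calling the texts irreconcilable. It does not remove the defect. The benefit/risk clause follows a sentence about remaining in or starting the study, and the postponement bullet is not made subject to it. The narrower meaning about switching therapies is not stated, and no time limit on the pause is given.

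A reader might go further and infer that screened participants are left with no rescue provision. The documents do not support that: Section 6.9.1 does not reach them, but the Section 1.3 footnote and Section 6.9 both contemplate treatment during screening and attach only a trial consequence to it. A reader might also suppose that *postponed* is a slip for a word such as *proposed*. That would fit the sentence, but it is a guess, and the point does not depend on it.

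**Conclusion.** The point holds as a minor wording defect in an operative instruction on participant care. Read literally, Section 10.9 advises deferring treatment outside the trial when study drug may be unavailable, without an exception for medical need and without saying how this fits with the treating physician's judgment.

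Its size is one clause in one contingency appendix. It takes effect only in a declared emergency, when a site cannot follow the protocol, and after Sponsor agreement. The documents do not show any group being denied care under the protocol's other rules. They also give no basis for inferring an effect on sample size, type I error, power or any estimate, and none is claimed. The conclusion rests on reading the bullet as written; if the sponsor meant something narrower, the text should say so.

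**What to change.** Replace the bullet so that it pauses trial activities only. Suggested wording: *If the site cannot adequately carry out protocol procedures during the emergency, only screening/enrollment and dosing with study intervention may be paused. Treatment outside the trial should be considered when medically needed in the treating physician's judgment. Sections 6.9, 6.9.1 and 7.1.1 continue to apply.*

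At minimum, keep the sentence and add *unless medically needed in the treating physician's judgment*. This short form suits a sponsor who does want to discourage elective switching during a pause.

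Neither version authorises prohibited medication. The Section 6.9 list and re-screening rule stay in place, and if a selected prohibited medication is used before Week 24, the worst-possible-score rule in Section 9.2.2.2 applies as it does now.

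The cost is one bullet at the next amendment. No new procedure, data field or analysis is needed, because Section 6.9 already requires the reason, dates and dosage of any medication received during the study to be recorded.

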10.10 APPENDIX 10: CLINICAL OUTCOMES ASSESSMENTS

10.10.1 CRSwNP Nasal Symptom Diary

The following questions will ask you to rate your nasal disorder symptoms over the past 24 hours. Please make sure you assess your nasal symptoms shortly after getting up in the morning (before 12:00 noon).

Rate the symptoms over the past 24 hours using the following ratings:

0 = No symptoms.

1 = Mild symptoms (symptoms clearly present, but minimal awareness and easily tolerated).

2 = Moderate symptoms (definitive awareness of symptoms that is bothersome but tolerable).

3 = Severe symptoms (symptoms that are hard to tolerate, cause interference with activities of daily living).

Please rate your nasal congestion/obstruction symptoms over the past 24 hours

- No symptoms
- Mild symptoms
- Moderate symptoms
- Severe symptoms

Please rate your loss of sense of smell symptoms over the past 24 hours

- No symptoms
- Mild symptoms
- Moderate symptoms
- Severe symptoms

Please rate your runny nose symptoms over the past 24 hours

- No symptoms
- Mild symptoms
- Moderate symptoms
- Severe symptoms

Please rate your post-nasal drip (dripping at the back of your nose) symptoms over the past 24 hours

- No symptoms
- Mild symptoms
- Moderate symptoms
- Severe symptoms

Please rate your facial pain/pressure symptoms over the past 24 hours

- No symptoms
- Mild symptoms
- Moderate symptoms
- Severe symptoms

Please rate your headache over the past 24 hours

- No symptoms
- Mild symptoms
- Moderate symptoms
- Severe symptoms

10.10.2 SNOT-22

I.D.: _____ **SINO-NASAL OUTCOME TEST (SNOT 22)** DATE: _____

Below you will find a list of symptoms and social/emotional consequences of your rhinosinusitis. We would like to know more about these problems and would appreciate your answering the following questions to the best of your ability. There are no right or wrong answers, and only you can provide us with this information. Please rate your problems as they have been over the past two weeks. Thank you for your participation. Do not hesitate to ask for assistance if necessary.

1. Considering how severe the problem is when you experience it and how often it happens, please rate each item below on how “bad” it is by circling the number that corresponds with how you feel using this scale: →	No Problem	Very Mild Problem	Mild or slight Problem	Moderate Problem	Severe Problem	Problem as bad as it can be		5 Most Important Items
1. Need to blow nose	0	1	2	3	4	5		
2. Nasal Blockage	0	1	2	3	4	5		
3. Sneezing	0	1	2	3	4	5		
4. Runny nose	0	1	2	3	4	5		
5. Cough	0	1	2	3	4	5		
6. Post-nasal discharge	0	1	2	3	4	5		
7. Thick nasal discharge	0	1	2	3	4	5		
8. Ear fullness	0	1	2	3	4	5		
9. Dizziness	0	1	2	3	4	5		
10. Ear pain	0	1	2	3	4	5		
11. Facial pain/pressure	0	1	2	3	4	5		
12. Decreased Sense of Smell/Taste	0	1	2	3	4	5		
13. Difficulty falling asleep	0	1	2	3	4	5		
14. Wake up at night	0	1	2	3	4	5		
15. Lack of a good night’s sleep	0	1	2	3	4	5		
16. Wake up tired	0	1	2	3	4	5		
17. Fatigue	0	1	2	3	4	5		
18. Reduced productivity	0	1	2	3	4	5		
19. Reduced concentration	0	1	2	3	4	5		
20. Frustrated/restless/irritable	0	1	2	3	4	5		
21. Sad	0	1	2	3	4	5		
22. Embarrassed	0	1	2	3	4	5		

2. Please mark the most important items affecting your health (maximum of 5 items) _____ ↑

SNOT-20 Copyright © 1996 by [name]., Washington University School of Medicine, St. Louis, Missouri
SNOT-22 Developed from modification of SNOT-20 by National Comparative Audit of Surgery for Nasal Polyposis and Rhinosinusitis
Royal College of Surgeons of England.

